1.4.2. Exclusion Criteria

Individuals are not eligible to participate in this study if they have met or meet any of the following exclusion criteria at either the Screening Visit or the Baseline Visit, unless otherwise stated:

- 1. History of allergies or adverse reactions to any of the excipients in the study drug formulation
- 2. Females who are pregnant or nursing or plan to become pregnant during the study.
- 3. Subjects with clinically significant gastrointestinal, renal, hepatic, neurologic, hematologic, endocrine, oncologic, pulmonary, immunologic, psychiatric, or

- CV/ischemic disease or any other condition that, in the opinion of the investigator, would jeopardize the safety of the subject or impact the validity of the study results.
- 4. Any clinically significant medical or psychiatric condition or medical history that, in the opinion of the investigator or the medical monitor, would interfere with the subject's ability to participate in the study or increase the risk of participation for that subject.
 - Note: Lumbar punctures will be performed but may be skipped for an individual subject if the investigator deems it appropriate, and after discussion with the medical monitor. Subjects with a contraindication to lumbar punctures, such as but not limited to space-occupying lesion with mass effect, increase of intracranial pressure due to increased CSF pressure, posterior fossa mass, Arnold-Chiari malformation, anticoagulation medication use, coagulopathy, uncorrected bleeding diathesis, congenital spine abnormality, previous adverse event associated with a lumbar puncture or skin infection at the puncture site, should not undergo the lumbar punctures as listed in the Schedule of Events. These subjects may still enroll in the study and should undergo all other study procedures.
- 5. Hepatic insufficiency, defined as liver function tests (LFTs) (i.e., AST and/or ALT) ≥3× the upper limit of normal (ULN), or bilirubin ≥1.5× the ULN (except in the case of Gilbert's disease)
- 6. Moderate or worse renal insufficiency, defined as an estimated glomerular filtration rate (eGFR) of <60 mL/min.
- 7. Current participation in any other investigational study with an investigational product or participation within 30 days prior to the start of the Screening Period or 5 half-lives of the previously taken investigational drug, whichever is longer.
- 8. History of alcohol or drug abuse within the last 6 months prior to the start of the Screening Period or current evidence of substance dependence
- 9. Any surgery within 30 days prior to the start of the Screening Period that may affect the subject's ability to complete all study procedures.
- 10. Subject has previously received PTC857.
- 11. Subject is receiving a combination of edaravone and sodium phenylbutyrate/taurursodiol treatment, where applicable, within 30 days prior to the start of the Screening Period
- 12. For female subjects, any past medical history of breast cancer, regardless of remission status, or any first degree relative with history of breast cancer
- 13. Subjects is taking a non-approved form of sodium phenylbutyrate and/or taurursodiol for the treatment of ALS.

1.5. Sample Size

For the primary efficacy endpoint, the combined assessment of ALSFRS-R and survival after 24 weeks of treatment, 307 subjects in the ITT1 Analysis Set (205 in the PTC857 group and 102 in the placebo group, based on a 2:1 randomization ratio) will provide approximately 85% power to detect a treatment difference of 2 points with a standard deviation of 5.3, based on a 2-sided 0.05 level Joint Rank Test, and assuming 24-week survival rates of 96.5% and 95% in the PTC857 and placebo groups, respectively. These assumptions took into consideration data from 2 clinical

studies in ALS which reached statistical significance for their primary endpoints that reported overall death rates of 0% and 5% (Edaravone (MCl-186) ALS 19 Study Writing Group 2017 and Paganoni, 2020) A standard deviation of 5.3 points for the ALSFRS-R score at Week 24, among treated subjects was reported for the edaravone study (Edaravone (MCl-186) ALS 19 Study Writing Group 2017).

Assuming approximately 10% of randomized subjects will not meet the ITT1 Analysis Set definition, then approximately 340 subjects will be randomized to ensure that 307 subjects are randomized into the ITT1 Analysis Set. Given that the primary analysis incorporates deaths as a combined endpoint, and a fully imputed analysis dataset is utilized in the analysis, additional enrollment and randomization to make up for discontinued subjects is not planned. This document clarifies a typographical error in the study protocol that incorrectly indicated a treatment difference of 2.5 points instead of 2 points, is of interest.

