3.4. Sample Size Justification

For the primary efficacy endpoint, the combined assessment of ALSFRS-R and survival after 24 weeks of treatment, 307 subjects in the ITT1 Analysis Set (205 in the PTC857 group and 102 in the placebo group, based on a 2:1 randomization ratio) will provide approximately 85% power to detect a treatment difference of 2.5 points with a standard deviation of 5.3, based on a 2-sided 0.05 level Joint Rank Test, and assuming 24-week survival rates of 96.5% and 95% in the PTC857 and placebo groups, respectively. Data from the 2 recently conducted clinical studies in ALS reported overall death rates of 5% and 0% (Edaravone (MCl-186) ALS 19 Study Writing Group 2017, Paganoni 2020). In addition, the edaravone study reported a standard deviation of 5.3 points for the ALSFRS-R score at Week 24, among treated subjects. Assuming approximately 10% of subjects will not meet the ITT1 Analysis Set definition, then approximately 340 subjects will be randomized to ensure that 307 evaluable subjects are randomized into the ITT1 Analysis Set. Given that the primary analysis incorporates deaths as a combined endpoint, and a fully imputed analysis dataset is utilized in the analysis, additional sampling for missing data is not planned.

If the attrition rate during the study is higher than expected, additional subjects may be enrolled in order to achieve the planned number of evaluable subjects.

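### The 85% power assumes an observed Week 24 ALSFRS-R for every survivor, and imputing missing scores is not a valid reason to make no allowance for them

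*SAP*

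**What the plan says.** SAP (Part A) Section 1.5 states that 205 PTC857 and 102 placebo subjects in ITT1 "will provide approximately 85% power to detect a treatment difference of 2 points with a standard deviation of 5.3". The calculation is for a joint rank test, two-sided at 5%, with survival to Week 24 taken as 96.5% on PTC857 and 95% on placebo. The SAP explains that the protocol "incorrectly indicated a treatment difference of 2.5 points instead of 2 points". The step from 307 to about 340 randomized subjects covers the 10% expected to fall outside ITT1.

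For missing Week 24 scores nothing is added, for two reasons. One is that deaths already count in the outcome. The other is that "a fully imputed analysis dataset is utilized in the analysis, additional enrollment and randomization to make up for discontinued subjects is not planned". The protocol synopsis and Protocol Sections 3.4 and 8.2 reason the same way: "a fully imputed analysis dataset is utilized in the analysis, additional sampling for missing data is not planned". Protocol Section 3.4 alone goes on to allow more subjects to be enrolled if attrition turns out higher than expected. Neither document says what attrition is expected.

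SAP Sections 4.7, 5.1 and 5.5.1.2 set out the missing-data method: missing at random, 100 imputations, results pooled by Rubin's rule.

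**The concern.** The two reasons are not of equal merit. A death is an outcome that the ranking uses directly, so it needs no allowance. A survivor without a Week 24 score is different, because that rank has to be predicted. Imputation keeps the subject in the dataset, but the uncertainty of the prediction is charged to the standard error. A complete rectangular dataset therefore does not carry complete information.

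What is at stake is how the stated power is read. Someone interpreting a result just short of significance would take 85% as the power of the design after dropout. The text gives a reason to believe that, and the reason is wrong.

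**Working it through.** **Inputs (SAP Section 1.5).** Difference 2 points, SD 5.3, n = 205 and 102, 24-week survival 96.5% and 95%, two-sided alpha 0.05.

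**Step 1: reproduce the stated figure.** The normal approximation for two means is power = Φ(δ / [σ√(1/n₁ + 1/n₀)] − 1.96).

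- √(1/205 + 1/102) = 0.1212, and 5.3 × 0.1212 = 0.642.
- 2 / 0.642 = 3.114, and Φ(3.114 − 1.96) = 87.6%.
- With the rank-test efficiency 3/π: 3.114 × √0.955 = 3.043, and Φ(3.043 − 1.96) = 86.1%.
- Simulating the joint rank test itself (deaths ranked lowest by time, survivors by a normal change score, complete data, 20,000 trials) gives 85.0%.

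So the stated 85% is a complete-data figure without covariates. With 2.5 points the same simulation gives about 96%, which supports the SAP's correction to 2.

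**Step 2: check for a reserve elsewhere.** 340 × 0.90 = 306. The step to 340 is used up by the ITT1 definition and leaves nothing for missing scores.

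**Step 3: what Rubin's rule does.** The total variance is T = W + (1 + 1/M)B, where W is the within-imputation and B the between-imputation variance. With no missing scores B = 0. With any missing, B > 0 and T exceeds the variance that complete data would give.

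**Step 4: size of the loss.** The dropout rates here are assumptions. If a fraction m of the information is lost, starting from 85%, power = Φ((1.960 + 1.036)√(1 − m) − 1.960). Reaching exactly 80% needs m = 1 − (2.802/2.996)² = 12.6%.

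Two cases were simulated. In the first, missing subjects contribute nothing. In the second, sequential regression imputation uses treatment and earlier visits and is pooled by Rubin's rule. The second case assumes random slopes over six visits, SD 5.3 at Week 24 and dropout spread evenly over visits. It combines two sets of simulations (1,200 or 4,000 trials per setting, 20 or 10 imputations, Monte Carlo standard error about 1.1 or 0.6 points).

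| Missing Week 24 scores (assumed) | Nothing recovered | Imputation with earlier visits |
|---|---|---|
| 0% | 85% | 85-86% |
| 10% | 81% | 81-83% |
| 15% | 79% | 80-82% |
| 20% | 77.5% | 79-82% |
| 30% | 71% | 74-78% |

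As a cross-check, the share of total variance due to missingness averaged 6-7% at 10% missing and 11-15% at 20%. The formula gives Φ(2.996√0.935 − 1.960) = 82.6% for a 6.5% loss. For losses of 11% and 15% it gives 80.7% and 78.9%. These agree with the table to within simulation error.

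**Step 5: covariate offset.** The primary ANCOVA (SAP Section 5.1) adjusts for baseline ALSFRS-R, TRICALS and the stratification factors. If these explain a share R² of rank variance, replace √(1 − m) by √((1 − m)/(1 − R²)). With R² = 10%, also an assumption, a 10% information loss gives 85.0% and a 12.6% loss gives 84.0%.

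**The case against.** The strongest reply has four parts.

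- **Covariates.** The planned model is more efficient than the test behind the 85%, and Step 5 shows that a modest R² would cancel a loss of about 10%. TRICALS includes the prior progression rate, so some explanatory value is likely. This stands, and it is why no loss of net power can be asserted. But it is not the argument the documents make, and SAP Section 3.5 leaves open dropping the stratification factors if strata are sparse.
- **Follow-up.** Subjects who stop drug are asked to complete visits (Protocol Sections 3.7, 4.6 and 6.4). Consenting early terminators are to have ALSFRS-R and vital status about every 28 days (Protocol Table 1, note d). Early-termination or unscheduled scores from Days 155 to 182 can serve as Week 24 (SAP Section 4.9). This also stands: stopping drug need not mean a missing score. It limits the missing rate but does not make the missing scores cost-free.
- **Extra enrolment.** Protocol Section 3.4 offers a remedy for high attrition. However, SAP Section 1.5 says that none is planned, and the trigger is undefined.
- **Milder reading.** The SAP sentence may mean only that no ITT1 subject leaves the analysis, so N stays 307. That is true of the headcount. The sentence is nevertheless offered as the reason why a power statement needs no allowance, and it does not support that.

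A reader might go further and infer that power falls to about 80%, or that the trial is too small. The documents do not support either. The first needs a dropout rate that they do not give, and both ignore the covariates and the retention measures.

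**Conclusion.** The point holds as a fault in the justification and labelling of the power, not as proof of inadequate size. The 85% is correct for complete Week 24 data in survivors with no covariate credit, and the imputation rationale does not extend it to incomplete data. Before any covariate gain, the cost is about 2 to 4 points at 10% missing, 3 to 5 at 15%, 3 to 6 at 20% and 7 to 11 at 30%.

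These figures rest on assumed dropout rates, missing-at-random dropout spread evenly over visits, and random-slope data. The planned imputation model also uses baseline variables, which the simulation did not, so recovery could be somewhat better. Covariate adjustment could remove some or all of the loss at the lower rates.

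**What to change.** In SAP (Part A) Section 1.5, and in the protocol synopsis and Protocol Sections 3.4 and 8.2:

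1. Delete the imputation rationale and keep the one about deaths.
2. State that 85% assumes complete Week 24 data in survivors and takes no credit for covariates.
3. Give the power at a named expected missing rate, with the assumptions used. If covariate adjustment is relied on to offset the loss, say so and state the variance it is assumed to explain.
4. Reconcile Protocol Section 3.4, which permits extra enrolment if attrition is higher than expected, with SAP Section 1.5, which plans none. The SAP's statement that it supersedes the protocol covers analysis, so it does not clearly settle a question of enrolment.

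The cost is a few sentences and a slightly less favourable power statement. The sample size, estimand, model and test stay as they are.

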1.6. Randomization and Blinding

Double-Blind 24-Week Treatment Period (Part A):

Subjects who satisfy all the inclusion and none of the exclusion criteria will be randomly assigned in a 2:1 ratio to receive one of the following two treatment arms during the 24-week treatment phase according to a study randomization scheme:

- Arm 1: PTC857 (250 mg) administered orally BID for 24 weeks.
- Arm 2: Matching placebo administered orally BID for 24 weeks.

Investigators and site staff will be blinded to treatment assignments during the entire study period. Biostatistics staff who are directly involved in the analysis of the study results and members of the clinical study team will remain blinded to the treatment assignment throughout the conduct of Part A and will be unblinded after database lock for Part A.

2. ANALYSIS SETS

2.1. All Enrolled Set

The All-Enrolled set will contain all subjects who signed an informed consent for this study. This analysis set will be used to summarize subject disposition.

2.2. Intent-to-Treat (ITT) Analysis Sets

Intent-to-Treat 1 Analysis Set (ITT1)

All subjects who are randomized after the Screening Period and take at least 1 dose of double-blind study drug in the Treatment Period and who have a decrease in the ALSFRS-R score of ≤4 points during the Screening Period will be included in the ITT1 Analysis Set. The ITT1 Analysis Set will be used for analysis of the primary endpoint. Subjects will be analyzed according to their randomized treatment.

Intent-to-Treat 2 Analysis Set (ITT2)

All subjects who are randomized after the Screening Period and take at least 1 dose of double-blind study drug in the Treatment Period will be included in the ITT2 Analysis Set. Subjects will be analyzed according to their randomized treatment assignment. ITT2 analysis set will be used as supportive analysis population.

2.3. Safety Set

All subjects in the ITT2 Analysis Set who receive at least 1 dose of study drug will be included in the Safety Analysis Set. Subjects will be analyzed according to the actual treatment received.

2.4. Per Protocol Set

All subjects in the ITT1 Analysis Set who have no major protocol deviations that affect the validity of the efficacy measurements will be included in the PP Analysis Set. The PP Analysis Set will be used for sensitivity analysis of the efficacy endpoint. Classification of whether protocol deviations require exclusion from the ITT1 set will be assessed at a Blinded Data Review Meeting (BDRM) prior to database lock. Subjects who meet the following criteria will be excluded from the ITT1 population hereby forming the per-protocol analysis set:

- (1) Received a protocol prohibited concomitant medication during the double-blind period.
 - a. Received edaravone and sodium phenylbutyrate/taurursodiol in combination,
 - b. Received a non-approved form of sodium phenylbutyrate/taurursodiol,
 - c. Initiated a new approved ALS therapy during the double-blind period.
- (2) Received study treatment different from the randomized treatment throughout the double-blind period
- (3) Significant non-compliance to study drug
- (4) Had significant inclusion or exclusion criteria violations
- (5) Had protocol deviations which may confound results of study treatment effectiveness
- (6) ALSFRS-R assessment on day -56, day 1 or day 169 performed by a non-certified rater.

This population will be to analyze the primary efficacy endpoint as supportive efficacy analysis. A separate document listing subjects excluded from the ITT1 population and reasons for exclusion will be finalized prior to treatment unblinding.

2.5. Pharmacokinetic Analysis Set

All subjects in the ITT2 Analysis Set who have at least 1 measurable post-baseline plasma or CSF PTC857 concentration will be included in the PK Analysis Set. Subjects with protocol violations that could affect the PK parameters will be assessed by the pharmacokineticist for inclusion into the PK analysis set. The pharmacokineticist may also exclude subjects or specific concentrations from the PK parameter calculation if required, for example if doses were missed or if samples were collected out of the allowed assessment windows. PK summaries and analyses will be conducted using the PK analysis set. The PK analysis set will be based on the actual treatment received.

2.6. Protocol Deviations

A protocol deviation is defined as any intentional or unintentional change to, or noncompliance with, the approved protocol procedures or requirements. Deviations may result from the action or inaction of the subject, investigator, or site staff. Examples of deviations include, but are not limited to, the following:

- Failure to adhere to study exclusion and inclusion criteria
- Failure to comply with dispensing or dosing requirements
- Use of medications that are specifically prohibited in the protocol
- Missed or out-of-window visits
- Drug dosing not administered within the time frame specified in the protocol
- Failure to adhere to test requirements, including vital signs, laboratory tests, physical examinations, PK blood draws, medical history, etc. (either the tests were not done, the incorrect tests were done, or the tests were not done within the time frame specified in the protocol)
- Procedural deviations such as incorrect storage of study drug, failure to update the ICF when new risks become known, or failure to obtain IRB/IEC approvals for the protocol and ICF revisions

Major protocol deviations are defined in the study's Protocol Deviation Handling Plan and include quality issues that have a high likelihood to significantly impact a subject's rights, safety or well-being, or have a potentially significant impact on data integrity.

Protocol deviations will be documented separately in a stand-alone file before database lock which include deviation category (e.g., violation of inclusion and exclusion criteria at screening, use of excluded concomitant medications, received the wrong treatment or incorrect dose), deviation description, severity (minor/major), visit/time point for each deviation.

Protocol deviations pertaining to the effects of the COVID-19 pandemic and related measures may be seen on this trial, and there may be an increase in the number of deviations seen due to the pandemic. All discussions pertaining to the COVID-19 pandemic and related protocol

deviations affecting inclusion/exclusion of analysis sets, and any adjustments to data handling and/or analysis of data will be documented in the blinded data review meeting (BDRM) Report. Both the BDRM Report and this document (SAP) will be finalized before database lock. A bysubject listing of major and minor protocol deviations will be provided for the safety analysis set.

3. GENERAL CONSIDERATIONS

3.1. General Considerations

Continuous data will be summarized using number of observations (n), arithmetic mean (mean), standard deviation (SD), median, minimum value (min) and maximum value (max) by treatment group. Additionally, for biomarker data, the summaries will include geometric means and standard deviations, as appropriate. Categorical variables will be summarized using the frequency count (n) and percentage (%) by treatment group. An overall/total group (i.e., sum of all treatment groups) will generally be presented additionally for summaries of disposition, demography, and baseline characteristics.

For all percentage calculations, the denominator will be the number of subjects in the analysis set for the treatment group, unless otherwise stated.

Only data from protocol scheduled visits will be included in the summary tables. Data from unscheduled visits will not be included in the summary tables but will be included in the by-subject listings. Descriptive summaries by visit and treatment will be provided for all the primary and secondary efficacy endpoints.

3.2. Data Definitions and Analysis Issues

3.2.1. Study/Onset Day

The study/onset day will be defined as the number of days since the first dose of study drug, which is assigned as Day 1 for analysis purposes. Study/onset day is calculated using the formula below:

Assessment Date Relative to First Dose of Study Drug	Study Day Calculation
Assessment/Event date prior to date of first dose	Date of assessment – Date of first dose of study drug
Assessment/Event date on or after Date of first dose	(Date of assessment – Date of first dose of study drug) +1

3.2.2. Baseline Definition and Change from Baseline

The Baseline Visit will be defined as Day 1 of the study. Unless otherwise stated, for each subject, baseline value of a parameter is defined as the last non-missing measurement taken at most one week prior to the first dose of study drug (including unscheduled assessments). If the last non-missing measurement and the date of first dose of study drug coincide, that measurement will be considered baseline, but AEs and medications commencing on the date of first dose of study drug will be considered post-baseline.

For the purposes of calculating summary statistics of the outcome measures, change from baseline will be derived as follows:

• Change from baseline = Post-baseline value – Baseline value

3.2.3. **Duration of Event**

Where the duration of an event is to be calculated, it will be derived as:

Duration (days) = (Event stop/end date – Event start date) + 1.

Duration (months) = Duration (days) / 30.4375

3.2.4. Retest and Unscheduled Visits

Unscheduled measurements and retests will not be included in by-visit summaries but will contribute to incidence of significant abnormality tables, where applicable.

In the case of a retest (same visit number assigned), the last available measurement for that visit will be used for by-visit summaries. Data listings will include all assessments, both scheduled and unscheduled.

